8.10.7.2. Cardiac Progression-Free Survival

Cardiac progression is defined as NT-proBNP progression of >30% increase and >300 ng/L increase or death. Cardiac progression will not be evaluated in the presence of renal progression, defined as an eGFR of < 30 mL/min/1.73 m², according to [Comenzo 2012 \(Appendix 2\)](#).

Progression-free survival is defined as the time from first infusion of study drug to the earliest of:

- first documented date of disease progression (as defined by NT-proBNP [Section 2.3.4.1.1]) or
- withdrawal from treatment or study due to organ (cardiac) progression or
- death on the study or
- death following withdrawal from treatment due to any cause.

Progression-free survival will be calculated in days as the earliest of the above dates (disease progression or death) minus the date of first infusion of study drug plus 1.

Subjects who are alive with no documented progression prior to the end of the study will be censored at the earliest of their date of the first assessment that meets renal progression (defined as an eGFR of < 30 mL/min/1.73 m²), date of the last NT-proBNP measurement, or date they withdraw consent or are lost to follow-up.

NEOD001 will be compared to placebo using the log rank test stratified by the randomization stratification factors. KM estimates of the distribution of the time-to-event will be tabulated and graphed by treatment group. The tabulation will include the KM estimate of the medians, 25th and 75th percentiles, and corresponding 95% CIs, if estimable. The tabular and graphical summaries will include the at-risk counts for every visit. The number and percent of subjects

censored and with events will be presented overall and for each visit, using last day of the visit window. The hazard ratio and 95% CI will be determined based on a Cox regression model stratified by randomization strata to estimate the magnitude of the effect.

In addition, a sensitivity analysis will be performed counting death or progression without subsequent response as an event.

8.10.7.3. Duration of Cardiac Response

Cardiac response is defined as >30% decrease and >300 ng/L decrease in NT-proBNP from baseline.

Duration of cardiac response is defined for subjects experiencing response as the time from the earliest cardiac response to the first documented date of disease progression, as defined by NT-proBNP progression of >30% increase and >300 ng/L increase. Subjects without response will be excluded from this analysis.

Duration of Cardiac Response will be calculated in days as the date of disease progression minus the date of first response plus 1.

Subjects will be censored at their date of the last NT-proBNP measurement if they complete the study or discontinue with no documented progression.

NEOD001 will be compared to placebo using the log rank test stratified by the randomization stratification factors. KM estimates of the distribution of the time-to-event will be tabulated and graphed by treatment group. The tabulation will include the summary statistics as described for continuous variables in Section 4.1, KM estimate of the medians, 25th and 75th percentiles, and corresponding 95% CIs, if estimable. The tabular and graphical summaries will include the at-risk counts for every visit. The number and percent of subjects censored and with events will be presented overall and for each visit, using last day of the visit window. The hazard ratio and 95% CI will be determined based on a Cox regression model stratified by randomization strata to estimate the magnitude of the effect.

In addition, a sensitivity analysis will be performed for subjects experiencing response as the time from the earliest cardiac response to the first documented date of disease progression without subsequent response.

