2.3.4.7. Additional Time-to-Event Endpoints

- Time to All-Cause Mortality (Overall Survival): Any after the first infusion of study drug (i.e. study day 1) through the study's last subject last visit (LSLV). Time (months) to event will be calculated as: (date of death - the date of first study drug infusion + 1) / 30.4375. Subjects will be censored at their last assessment known to be alive prior to LSLV.
- Progression free survival: Time (days) to event will be calculated as the earliest of event dates (cardiac disease progression or death) minus the date of first infusion of study drug plus 1.

- Duration of Cardiac Response: Time (days) to event will be calculated as the earliest date of disease progression subsequent to the first response minus the date of first response plus 1. Subjects never achieving response are excluded.
- Time to derived organ progression for each organ (cardiac, renal) separately
- Time to cardiac or renal progression
- Time to first organ response for each organ (cardiac, renal) separately
- Time to cardiac or renal response

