3. SAMPLE SIZE JUSTIFICATION

For the primary endpoint, the assumed true rates for NEOD001 vs placebo are 50% and 22.5%, respectively. Based on a two-sample comparison of proportions at the $\alpha=0.05$ level of significance, a total sample size of 100 subjects (50 in the NEOD001 arm, 50 in the placebo arm) will provide $>80\%$ power based on a two-sided Cochran-Mantel-Haenszel (CMH) test. Based on the actual enrolled sample size ($N\sim 130$), the final power is 91%.

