
Time-to-event data will be summarized using Kaplan-Meier (KM) methodology using 25th, 50th (median), and 75th percentiles with associated 2-sided 95% CIs (where estimable), as well as percentage of censored observations.

All statistical tests comparing groups will be conducted at the 2-sided, 0.05 level of significance, unless otherwise specified. Summary statistics for each treatment group will be presented, as well as two-sided 95% CIs comparing groups will be provided.

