8.10.8. Other Efficacy Analyses

8.10.8.1. Cardiac Hospitalizations

Hospitalization reason will be coded using MedDRA version 19.0. Any adverse event with a preferred term in the broad standardized MedDRA query (SMQ) definition of Cardiac Failure or in the SMQ definition of Cardiac Arrhythmias that results in hospitalization will be counted as a Cardiac Hospitalization.

Time to first cardiac hospitalization admission will be calculated in days as the date of first cardiac hospitalization admission minus the date of first study drug infusion plus 1. Subjects who do not experience an event will be censored at the date of last contact. NEOD001 will be compared to placebo using the same methods described in Section 8.10.7.1. In addition, the time to recurrent cardiac hospitalization, i.e., time to next cardiac hospitalization after the first, will be analyzed in the same manner.

The number of cardiac hospitalizations per subject over the course of the study will be summarized both as a continuous and categorical variable by treatment group. A Poisson regression model will be fit using the continuous number of cardiac hospitalizations as the dependent variable, the total time in study as the offset variable, and treatment group as a factor. The number of cardiac hospitalizations per subject will be categorized as 0, 1, and ≥ 2 . The categorical variable will be analyzed using a CMH test stratified by the randomization stratification factors. The number and percentage, with associated two-sided 95% CIs, of subjects in each category will be presented by treatment group. An ordinal logistic regression

will be performed with categorical number of hospitalizations (0, 1, and ≥ 2) as the dependent variable and factors for treatment group and randomization strata.

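### Duration of cardiac response is tested between arms among responders only, so its p-value and hazard ratio are not randomized comparisons (minor; exploratory endpoint)

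*SAP*

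**What the plan says.** **Duration of response.** SAP 8.10.7.3 runs the clock from first cardiac response to NT-proBNP progression. On the analysis set it says "Subjects without response will be excluded from this analysis"; the endpoint definition in SAP 2.3.4.7 agrees: "Subjects never achieving response are excluded". It then states: "NEOD001 will be compared to placebo using the log rank test stratified by the randomization stratification factors". A Cox model stratified by the randomization strata supplies a hazard ratio with a 95% CI as the measure of effect size. On censoring: "Subjects will be censored at their date of the last NT-proBNP measurement if they complete the study or discontinue with no documented progression". The one sensitivity analysis changes the progression event but stays within responders. No caveat says that the comparison is not randomized. Under SAP 4.1 the default applies: "All statistical tests comparing groups will be conducted at the 2-sided, 0.05 level of significance, unless otherwise specified".

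**Hospitalization.** SAP 8.10.8.1 first analyses time to first cardiac hospitalization with the overall-survival methods, keeping event-free subjects in as censored. It then adds "the time to recurrent cardiac hospitalization, i.e., time to next cardiac hospitalization after the first, will be analyzed in the same manner". The time origin and risk set of this second analysis are not stated.

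**Status.** Both endpoints are listed as exploratory (SAP 2.3.4; protocol 3.2.4), outside the fixed testing sequence of SAP 8.6.

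**The concern.** NT-proBNP best response is the primary endpoint. Restricting duration to responders therefore selects subjects by the outcome the drug is meant to change. If NEOD001 works, its responders are a mixture of subjects who would have responded anyway and subjects who responded only because of the drug. Placebo responders come from the first group alone. If the second group holds its response less well, the NEOD001 curve among responders falls faster even though nobody is worse off. Stratifying by hematologic response and baseline NT-proBNP does not repair selection on a later outcome.

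At stake is one exploratory p-value and hazard ratio that would be read as a treatment effect and could have the wrong sign. The same reasoning would apply to time to next hospitalization if only subjects with a first admission enter it.

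**Working it through.** **1. The plan's figure.** SAP section 3 states that "the assumed true rates for NEOD001 vs placebo are 50% and 22.5%, respectively", with 91% power at about 130 subjects. With 65 per arm, pooled variance and two-sided 0.05:

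- null SE = √(2 × 0.3625 × 0.6375 / 65) = 0.0843
- alternative SE = √((0.50 × 0.50 + 0.225 × 0.775) / 65) = 0.0808
- power = Φ((0.275 − 1.96 × 0.0843) / 0.0808) = Φ(1.36) = 91%

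The stated figure is reproduced, so these rates and 65 per arm are used below.

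**2. Who is compared.** Expected responders are 65 × 0.50 = 32.5 on NEOD001 and 65 × 0.225 = 14.6 on placebo. That is 47.1 of 130, or 36%. Of the 50 percentage points responding on NEOD001, 50 − 22.5 = 27.5 would be drug-only responders with no placebo counterpart.

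**3. Can the direction go wrong?** The documents give no rates of losing response, so these are assumptions. Subjects who would respond on either arm (22.5%) lose response at 3% a month on placebo and 2.4% on drug (20% lower). Drug-only responders (27.5%) lose it at h a month. Over 7 months after response, with constant rate r, the probability of loss is 1 − e^(−7r) and mean months in response are (1 − e^(−7r))/r.

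- Placebo: 0.225 × 6.31 = 1.42 months in response, averaged over all subjects; loss rate among responders 0.030 a month.
- NEOD001, h = 10%: 0.225 × 6.44 + 0.275 × 5.03 = 2.83 months over all subjects. Loss rate among responders = (0.225 × 0.155 + 0.275 × 0.503) / 2.83 = 0.061 a month. Ratio 2.0.
- NEOD001, h = 5%: 3.07 months; rate 0.038; ratio 1.3.
- NEOD001, h = 3%: 3.19 months; rate 0.027; ratio 0.9.

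In every case the drug about doubles time in response over all subjects, yet the responder-only ratio runs from 0.9 to 2.0.

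**4. Simulation of the log-rank test.** 65 per arm, unstratified, with either 7 months' follow-up after response or response onset spread over months 1–6 or 1–9:

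| Drug-only loss per month | Points against NEOD001 | Significant against NEOD001 | Median rate ratio |
|---|---|---|---|
| 3% | 46–48% | about 1% | about 0.9 |
| 5% | 63–66% | 3–4% | about 1.3 |
| 10% | 86–90% | 13–17% | about 2.1 |

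**5. A different model.** Let an unmeasured severity score influence both response and later progression (assumed hazard 0.10 a month, log-hazard slope 0.5–1.0 per SD). The responder-only hazard ratio is then:

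| Severity–response correlation | True ratio 1.0 | True ratio 0.80 |
|---|---|---|
| 0 | 0.99–1.02 | 0.78–0.85 |
| 0.5 | 1.14–1.22 | 0.93–1.04 |
| 0.8 | 1.28–1.47 | 1.01–1.20 |

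Significance against NEOD001 occurs in 0.5–7% of trials, with about 11–22 events per trial.

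**6. Hospitalization, if only subjects with a first admission are at risk.** Assume 30% severe subjects (0.10 a month, no drug effect) and 70% mild subjects (0.02 a month, cut by 60%). First-admission risk over 12 months falls from 35.8% to 27.4%, yet the rate after the first is 1.19 times higher on NEOD001. If the drug cuts everyone's rate by the same factor, the ratio is only attenuated: a true 0.70 becomes 0.71–0.79, and a true 0.50 becomes 0.51–0.61.

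**The case against.** The strongest reply is that little depends on this. Both endpoints are exploratory with no alpha allocated, and with so few events significance in the wrong direction is uncommon. That stands, and it sets the severity.

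The second reply is that the SAP already has comparisons in all subjects. On the cardiac side these are best response by CMH (8.7), progression-free survival (8.10.7.2), time to cardiac progression (8.10.7.4) and time to first cardiac response (8.10.7.5). For hospitalizations (8.10.8.1) they are time to first, a Poisson model of counts with time in study as offset, and CMH and ordinal models of 0, 1 and ≥2. That stands too. A reader might infer that the arms are compared only within selected subsets; the documents contradict this.

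Third, a reader might infer that SAP 8.10.8.1 excludes subjects without a first admission. It has no exclusion sentence like that in 8.10.7.3, and analysis in the same manner as time to first could mean that everyone stays in from first infusion. Measuring to the next event after the first suggests the narrower set without settling it. This is a gap to close, not an established selection.

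None of these replies makes the responder-only test a randomized comparison. Exploratory status does not give its hazard ratio a causal meaning, and 8.10.7.3 presents it as a measure of effect.

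**Conclusion.** The point holds for SAP 8.10.7.3, at minor severity. As written, the p-value and hazard ratio compare about 32 with 15 subjects selected by the primary outcome, and they can penalise NEOD001 if drug-created responders are less durable.

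A reader might go further and conclude that the test will usually make a helpful drug look harmful. The documents do not support that. It takes drug-only responders losing response at about 10% a month against 2.4% for the other NEOD001 responders, and neither rate is in the documents. At 5% the tilt is modest. At 3% it is gone, as it is when severity and response are uncorrelated. The defensible statement is that the direction is unreliable, by an amount that cannot be known from the plan.

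For SAP 8.10.8.1 the point is conditional on the unstated risk set, and a reversal there also needs the benefit to differ between milder and more severe subjects. No primary, key secondary or sample-size conclusion changes.

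**What to change.** **SAP 8.10.7.3.** Keep the Kaplan-Meier estimates by arm among responders, label them descriptive and non-randomized, and remove the log-rank test and hazard ratio.

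If a between-arm comparison is wanted, compare time in response from first infusion through EEOS in all ITT subjects, with non-responders set to zero, by a van Elteren test stratified by the randomization strata. Define response as ending at the first visit that no longer meets the response criterion, or at death. This rule is needed because a subject can stop meeting the criterion without progressing, and because 8.10.7.3 does not list death as an event whereas 8.10.7.4 counts it as progression. State alongside it that about 64% of subjects (1 − 0.3625) would score zero at the planning rates, so the result will largely track the primary response comparison.

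**SAP 8.10.8.1.** State the time origin and risk set for time to next hospitalization. If only subjects with a first admission enter, make it descriptive too. Rely for comparison on the all-subject analyses already planned there: time to first, and the Poisson counts, preferably with robust variance, or a mean cumulative count.

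**Cost.** SAP wording and at most one added analysis from data already collected. The downside is that the responder-only p-value and hazard ratio are no longer shown.

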4. GENERAL STATISTICAL METHODS

4.1. Reporting Conventions

Individual subject data obtained from electronic case report forms (eCRFs), central laboratories, external sources, and any derived data will be presented in data listings by subject. The primary data source will be used for all analyses. All data listings that contain an evaluation date will contain a relative study day. Pre-treatment and on-treatment study days are numbered relative to the day of the first dose of study drug which is designated as Day 1. The preceding day is Day -1, the day before that is Day -2, etc.

All output will be incorporated into Microsoft Word rich text format (.rtf) files, sorted and labeled according to the ICH recommendations, and formatted to the appropriate page size(s).

For categorical variables, summary tabulations of the number and percentage of subjects within each category (with a category for missing data) of the parameter will be presented. Percentage calculations will be based on non-missing data, unless otherwise specified. Percentages are rounded to 1 decimal place, unless otherwise specified.

For frequency counts of categorical variables, categories whose counts are zero will be displayed for the sake of completeness. For example, if none of the subjects discontinued due to “lost to follow-up,” this reason will be included in the table with a count of 0. Percentages based on frequency counts will be presented to one decimal place, and values less than 1% will be presented as “<1%.” Values less than 100% but greater than 99% will be presented as “>99%.”

For continuous variables, the number of subjects, mean, standard deviation (SD), median, 25th (Q1) and 75th (Q3) quartiles, minimum, and maximum values will be presented. The precision of summary statistics, unless otherwise specified will be as follows: mean and median to 1 more decimal place than the raw data, and SD to 2 decimal places more than the raw data. In general, the number of decimal places should not exceed 3 decimal places unless appropriate. Confidence intervals (CIs) will be provided and will be rounded to 1 decimal place, unless otherwise specified, in the table and listing shell.

For tables where rounding is required, rounding will be done to the nearest round-off unit. For example, when rounding to the nearest integer, values $\geq XX.5$ will be rounded up to $XX+1$ (e.g., 97.5 will round up to 98), while values $<XX.5$ will be rounded down to XX (e.g., 97.4 will round down to 97).

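### The duration-of-cardiac-response table adds raw means, medians and quartiles to a censored endpoint without saying who is counted, and either reading understates duration

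*SAP*

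**What the plan says.** SAP 8.10.7.3 starts the duration at the earliest cardiac response and ends it at the first documented NT-proBNP progression: "Duration of Cardiac Response will be calculated in days as the date of disease progression minus the date of first response plus 1". Responders without progression are censored: "Subjects will be censored at their date of the last NT-proBNP measurement if they complete the study or discontinue with no documented progression".

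On the table it says: "The tabulation will include the summary statistics as described for continuous variables in Section 4.1, KM estimate of the medians", followed by the KM quartiles, with 95% CIs where estimable. The Section 4.1 statistics referred to are "the number of subjects, mean, standard deviation (SD), median, 25th (Q1) and 75th (Q3) quartiles, minimum, and maximum values". For time-to-event data, Section 4.1 separately prescribes: "Time-to-event data will be summarized using Kaplan-Meier (KM) methodology using 25th, 50th (median), and 75th percentiles".

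The same paragraph of 8.10.7.3 also requires a KM graph, at-risk counts, a stratified log-rank test and a stratified Cox model. It adds: "The number and percent of subjects censored and with events will be presented overall and for each visit".

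The tabulations in 8.10.7.1 (overall survival) and 8.10.7.2 (PFS) list KM quantities only, and 8.10.7.4 and 8.10.7.5 follow 8.10.7.1. Protocol 8.3.4 says the time-to-event endpoints are to be handled as PFS is. SAP Section 10 gives no reason for treating this table differently.

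**The concern.** A raw mean or median describes a duration only if every duration has been observed to its end. Here a responder who has not progressed contributes only a lower bound.

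The SAP leaves open which subjects enter the raw statistics:

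- **Reading A: all responders, with the censoring date used as the end date.** The raw figures then largely measure how much follow-up remained after the first response. An arm that responds sooner shows longer durations even if nobody in either arm loses response.
- **Reading B: progressors only.** The duration formula is written only in terms of a progression date, so this reading is open too. It leaves out exactly the responses that lasted.

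Two programmers could produce different tables from this text, and neither would estimate duration of response. When most responders are censored, the KM median may not be estimable. The raw figures could then be the only numeric durations in the table.

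**Working it through.** The documents give no figure for duration of response, so there is none to reproduce.

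**Inputs**

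- Visit days from SAP 4.6, Table 3: targets 28, 56, ..., 308 (Months 2 to 12) and EEOS at 338.
- One month is 30.4375 days (SAP 4.5).
- Duration is end date minus first-response date plus 1 (SAP 8.10.7.3).
- Assumed: NT-proBNP is measured at every visit and follow-up runs to Day 338. Subjects who stop early have a shorter remainder.
- Assumed: the distribution of first-response times, which the documents do not give.

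**Step 1. Reading A, nobody loses response.** A first response on Day t records 338 − t + 1 days. The twelve possible values are 311, 283, 255, 227, 199, 171, 143, 115, 87, 59, 31 and 1.

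With first response equally likely at each visit, the first eleven values sum to 11 × 171 = 1881. Adding 1 gives 1882, and 1882/12 = 156.8 days = 5.2 months. The raw median is (171 + 143)/2 = 157 days.

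**Step 2. Other response timings.** Visit k (k = 0 to 11) is given weight proportional to r^k, with r chosen so that the median first response falls on the stated day. Durability is still perfect.

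| Median first response (day) | Raw mean (days) | Months |
|---|---|---|
| 56 | 266.5 | 8.8 |
| 84 | 233.1 | 7.7 |
| 140 | 185.6 | 6.1 |
| 196 | 147.4 | 4.8 |
| 252 | 106.4 | 3.5 |

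The same true durability gives a figure that moves more than twofold on timing alone.

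**Step 3. Two groups differing only in timing.** For one subject, a first response 28 days later shortens the recorded duration by 28 days. With early weights (r = 0.8) and late weights (r = 1.2), again with perfect durability, the raw means are about 224 and 100 days.

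**Step 4. Both readings when responses do end.** Assume exponential durations with a true median of 730 days in both groups, so the true mean is 730/ln 2 = 1053 days. Progression is recorded at the next visit, and the timing weights are those of Step 3.

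| | Early responders | Late responders |
|---|---|---|
| Progress by Day 338 | 19% | 9% |
| Reading A, raw mean (days) | 202 | 94 |
| Reading B, raw mean (days) | 136 | 98 |
| KM probability still in response at about 170 days (simulated) | 0.855 | 0.855 |

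Both raw means fall far below 1053 days and differ between groups with identical durability. KM gives the same answer for both.

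**Why the direction is general.** Write T for the true duration and C for the follow-up left after response. Reading A averages the smaller of T and C, which never exceeds T. Reading B averages T only among subjects with T no longer than C. Both fall short whenever some responders are censored. Detection at the next visit lengthens recorded times slightly, but it does so for KM as well.

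**The case against.** A reader might infer that perfectly durable responses will be reported as lasting five months. The documents do not support this, for three reasons.

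- **The raw statistics do not stand alone.** The same table must show KM percentiles, at-risk counts and the number and percent censored. With perfect durability it would show 100% censored and KM percentiles that cannot be estimated, next to the raw mean.
- **The SAP does not say that censored times enter the mean.** Under Reading B the perfectly durable case has no observations, and the five-month figure disappears.
- **Five months is the value for evenly spread first responses.** No passage gives the actual timing.

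A reader might also infer that the plan compares early with late responders. It does not. The table is by treatment group, so the timing artefact shows only if the arms differ in when they respond. The contrast in Step 3 uses chosen weights, not expected data. Nor does 8.10.7.3 replace KM in breach of Section 4.1: it adds statistics to the KM summary.

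Finally, duration of response is exploratory (Protocol 3.2.4, SAP 2.3.4.7) and outside the testing hierarchy of SAP 8.6. The clause changes no test, hazard ratio or decision.

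All of this stands and limits the severity. It does not rescue the statistics themselves, because under neither reading do they estimate how long a response lasts. Response timing may also differ by arm: time to first response is itself an endpoint (SAP 8.10.7.5).

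**Conclusion.** The point holds as a minor defect. The clause attaches uncensored summaries to a censored endpoint and does not say who is counted, and both readings understate duration whenever some responders are censored.

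The size depends on assumptions. If censored times are counted, durability is perfect and follow-up is complete to Day 338, the raw mean is 5.2 months under evenly spread first responses and about 3.5 to 8.8 months under the other timings tried. The direction of the error, and the loss of 28 recorded days per 28-day delay for a subject censored on a fixed date, do not depend on the timing distribution. The inferential results for this endpoint, and the primary and key secondary conclusions, are untouched.

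**What to change.** In SAP 8.10.7.3, delete the words that bring the Section 4.1 continuous-variable statistics into the tabulation, so that the table matches 8.10.7.1 and 8.10.7.2.

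If the sponsor prefers to keep the statistics, label them as observed follow-up after first response and state whether they cover all responders or only those who progressed.

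KM probabilities of remaining in response at fixed times after first response would be a useful addition but are optional.

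The cost is one SAP sentence and one table shell. No data collection or patient procedure changes.
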